8.2.7. Ventilator-Free Days

The number of ventilator-free days from randomization through Day 28 will be summarized descriptively and analyzed using ANCOVA. The LS means will be presented along with the associated 95% CI within each treatment group. In comparing treatments, LS mean differences between treatments will be presented along with associated 95% CIs and p-values. In order to assign the worst total score for death, participants that die will have all days from randomization through day 28 treated as if they had been on a ventilator.

8.2.8. Hospitalization Days

The number of hospitalization days from randomization through Day 28 will be summarized descriptively and analyzed using ANCOVA. The LS means will be presented along with the associated 95% CI within each treatment group. In comparing treatments, LS mean differences between treatments will be presented along with associated 95% CIs and p-values. In order to assign the worst total score for death, participants that die will have all days from randomization through day 28 treated as if they had been in the hospital.

8.2.9. Organ Failure-Free Days

The number of organ failure-free days from randomization through Day 28 will be summarized descriptively and analyzed using ANCOVA. The LS means will be presented along with the associated 95% CI within each treatment group. In comparing treatments, LS mean differences between treatments will be presented along with associated 95% CIs and p-values. In order to assign the worst total score for death, participants that die will have all days from randomization through day 28 treated as if they had organ failure.

8.2.10. Days at Elevated Level of Care [ICU]

The number of days spent in the ICU from randomization through Day 28 will be summarized descriptively and analyzed using ANCOVA. The LS means will be presented along with the associated 95% CI within each treatment group. In comparing treatments, LS mean differences between treatments will be presented along with associated 95% CIs and p-values. In order to assign the worst total score for death, participants that die will have all days from randomization through day 28 treated as if they had been spent in the ICU.

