6.1.7. Derived Variables

- Respiratory failure is defined as the requirement for use of intubation/mechanical ventilation, an oxygen rate with high flow nasal cannula greater than 20 L/min, non-invasive positive pressure respiratory support, or ECMO, or clinical diagnosis of respiratory failure.
- Respiratory failure-free survival is defined as the combination of no respiratory failure (defined above) and no report of mortality from any cause.
- Mortality from any cause is defined as death listed on the Study Completion CRF or WHO 9-point ordinal scale assessment of death.
- Non-invasive positive pressure respiratory support is defined as the use of continuous positive airway pressure (CPAP) or bilevel positive airway pressure (BiPAP).
- Ventilator use is defined as the use of mechanical ventilation, CPAP, or BiPAP.
- Organ failure is defined as a reported AE indicating a ‘failure’ of respiratory, cardiovascular, hepatic, renal, coagulation, or neurological reported at the PT level or

‘insufficiency’ reported as the lowest level term.

- Renal stabilization or replacement is defined as reported use of any type of dialysis in concomitant medications with a route recorded as (“HEMODIALYSIS”, “PERITONEAL DIALYSIS”, or “DIALYSIS”).
- Time to initiation of supplemental oxygen or other respiratory support in the first 28 days after randomization = (the earliest of Day 28 or date/time of the first use – date/time of randomization) + 1.
- Duration of supplemental oxygen or other respiratory support in the first 28 days after randomization = (the earliest of Day 28 of the study or date/time of the last use – the latest of date/time of the first supplemental oxygen or other respiratory support or date/time of randomization) + 1.
- Time to initiation of intubation/mechanical ventilation, an oxygen rate with high flow nasal cannula greater than 20 L/min, non-invasive positive pressure respiratory support, ECMO in the first 28 days after randomization = (the earliest of Day 28 or date/time of the first support – date/time of randomization) + 1.
- Duration of intubation/mechanical ventilation, an oxygen rate with high flow nasal cannula greater than 20 L/min, non-invasive positive pressure respiratory support, or ECMO in the first 28 days after randomization = (the earliest of Day 28 of the study or date/time of the last specified respiratory support – the latest of date/time of the first specified respiratory support or randomization) + 1.

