The number of days of respiratory support meeting criteria outlined in the critical COVID criteria among patients that experience respiratory failure in the first 28 days from randomization through Day 28 will be summarized descriptively and analyzed using ANCOVA. The LS means will be presented along with the associated 95% CI within each treatment group. In comparing treatments, LS mean differences between treatments will be presented along with associated 95% CIs and p-values.

For study Part 1 analysis, this endpoint will be reported in all patients in the ITT population.

The time to start of respiratory support through Day 28 will be analyzed using a Cox-Proportional hazard model. The number of participants who experience the event and rate ratio with 95% CI will be presented. The p-value to test if the rate ratio between treatments differs from 1 will be evaluated. Kaplan-Meier methodology will be used to estimate the median time to the event and 95% CI. Censoring events include loss to follow-up prior to Day 28. Mortality will not be considered a censoring event and instead will be analyzed as if the patient was on the forms of supplemental oxygen for all days between randomization and Day 28. If mortality or the event of interest does not occur, all subjects will be censored at Day 28. Covariates will include those a priori specified in [Section 6.1.2](#), and Efron's method for handling tied time-to-events will be used. The p-value testing for non-zero treatment effect will be obtained from a Wald chi-square test, and the 95% CI associated with the treatment effect will be a Wald-type CI.

Duration and time to the forms of respiratory support through Day 28 will be calculated according to [Section 6.1.7](#).

In order to assign the worst total score for death, participants that die will have all days from randomization through Day 28 treated as if they were receiving critical COVID-level respiratory support (i.e., analyzed as having 28 days of COVID-level respiratory support) for these analyses. Participants that do not die but have missing data will not be excluded from the analysis of duration or time-to-event endpoints and will have an appropriate value assigned.

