8.2.11. Days Without Renal Stabilization

The number of days without renal stabilization from randomization through Day 28 will be summarized descriptively and analyzed using ANCOVA. The LS means will be presented along with the associated 95% CI within each treatment group. In comparing treatments, LS mean differences between treatments will be presented along with associated 95% CIs and p-values. In order to assign the worst total score for death, participants that die will have all days from randomization through day 28 treated as if they were on renal stabilization.

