8.2.12. Days of Oxygen Support

The number of days of oxygen support from randomization through Day 28 will be summarized descriptively and analyzed using ANCOVA. The LS means will be presented along with the associated 95% CI within each treatment group. In comparing treatments, LS mean differences between treatments will be presented along with associated 95% CIs and p-values. In order to assign the worst total score for death, participants that die will have all days from randomization through day 28 treated as if they were on oxygen support.

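### Eight Day 28 count rules and two time-to-event rules in the SAP put no date limit on death, so a death on Days 29–60, read literally, overwrites complete Day 1–28 data

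*SAP*

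**What the plan says.** Eight secondary outcomes are counted over the first 28 days, and each has a rule giving the worst total to a participant who dies:

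- For critical-level respiratory support, in 8.2.5: "participants that die will have all days from randomization through Day 28 treated as if they were receiving critical COVID-level respiratory support". The SAP adds that this means a score of 28 days.
- For ventilator-free days, in 8.2.7: "participants that die will have all days from randomization through day 28 treated as if they had been on a ventilator".
- For hospitalization days, in 8.2.8: "participants that die will have all days from randomization through day 28 treated as if they had been in the hospital".
- For organ failure-free days, in 8.2.9: "participants that die will have all days from randomization through day 28 treated as if they had organ failure".
- For ICU days, in 8.2.10: "participants that die will have all days from randomization through day 28 treated as if they had been spent in the ICU".
- For days without renal stabilization, in 8.2.11: "participants that die will have all days from randomization through day 28 treated as if they were on renal stabilization".
- For days of oxygen support, in 8.2.12: "participants that die will have all days from randomization through day 28 treated as if they were on oxygen support".
- For healthcare encounters, in 8.2.13: one encounter is assigned to every day.

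The Cox paragraphs in 8.2.4 and 8.2.5 say that mortality is not a censoring event and that the patient is analysed as on support for the whole period to Day 28. They give no date of death either.

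SAP 6.1.7 sets no time limit: "Mortality from any cause is defined as death listed on the Study Completion CRF or WHO 9-point ordinal scale assessment of death". The WHO scale is scored at Days 45 and 60 (Protocol 10.2.3.6 and 10.2.3.7), and SAP 8.2.2 analyses deaths through Day 60.

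Other death rules are bounded. SpO2 (8.2.6) is imputed only for a death within 28 days, and the WHO score of 8 (8.2.1) applies from the date of death onward. SAP 6.1.4 and Protocol 13.1 assign the worst value to data after death, and Protocol 13.1.4 to data missing because of death. Protocol 13.1.4 leaves the specific assignments to the SAP.

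**The concern.** In all eight sentences, Day 28 limits the days to be rescored and not the date of death. A participant who spends no day in the ICU, completes Day 28 and dies on Day 50 has died under 6.1.7, so the rule as written scores 28 ICU days. An event outside the endpoint's window then replaces complete observations inside it. Two programmers working from this text could produce different tables.

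One such death could change several outcomes at once. ICU days and days of oxygen support are key secondary endpoints (8.1.1). Hospitalization days, ICU days and encounters also feed the pharmacoeconomic review (8.3.2). SAP 10 now reports secondary outcomes for Part 1 with summary statistics and confidence intervals instead of listings alone. It also drops the respiratory-failure subset in 8.2.5 for Part 1, so a late death there would earn 28 days of critical-level support even in someone who never had respiratory failure.

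**Working it through.** **1. The plan's own figure.** Days 1 to 28 inclusive: 28 − 1 + 1 = 28, which matches the score stated in 8.2.5.

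**2. The same participant under three rules.** Assume 5 observed ICU days.

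| Day of death | 8.2.10 as written | 8.2.10 limited to deaths by Day 28 | 6.1.4 (data after death only) |
|---|---|---|---|
| 10 | 28 | 28 | 5 + (28 − 10) = 23 |
| 45 | 28 | 5 | 5 + 0 = 5 |

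For the Day 10 death, the specific rule goes beyond 6.1.4 by rescoring days before death. That is a stated choice. For the Day 45 death, the limited rule and 6.1.4 agree on 5, and only the literal rule gives 28.

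**3. Size of one late death.** Let d be the participant's observed days and n the arm size. The difference between the two readings of the raw arm mean is (28 − d)/n. For ventilator-free days, organ failure-free days and days without renal stabilization, the literal score is 0, so the mean falls by f/n, where f is observed free days.

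Arm sizes come from SAP 3.2: Part 1 is 5:5:5:3, and Part 2 is 72/2 = 36 per arm.

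| n | d = 0 | d = 10 | d = 20 |
|---|---|---|---|
| 5 (Part 1 varespladib arm) | 28/5 = 5.6 | 18/5 = 3.6 | 8/5 = 1.6 |
| 3 (Part 1 placebo arm) | 28/3 = 9.33 | 18/3 = 6.0 | 8/3 = 2.67 |
| 36 (Part 2 arm, if fully enrolled) | 28/36 = 0.78 | 18/36 = 0.50 | 8/36 = 0.22 |

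**4. Limits of the table.**

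- Everyone is hospitalized at entry, so d is at least 1 for hospitalization days. The largest shifts there are 27/5 = 5.4 and 27/3 = 9.0.
- For encounters, the formula assumes at most 28 observed. Above 28, the assigned value would lower the count.
- n = 36 does not fit 8.2.5 in Part 2, which uses the smaller respiratory-failure subset.
- Part 2 reports covariate-adjusted LS means, which move by roughly and not exactly these amounts.
- Deaths by Day 28 score the same under both readings.

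**5. Time-to-event paragraphs.** Under 8.2.4, a participant who needed no support and died on Day 50 is, read literally, analysed as on support from randomization. With the limit, that participant is censored at Day 28. The ambiguity is the same, although (28 − d)/n does not measure it.

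**The case against.** The best case against is that the window already supplies the limit. Each of these outcomes is defined over the 28 days after randomization, and the general rule covers only data after death, so a Day 50 death leaves nothing to impute. The SpO2 rule may show the intended convention; it also needs a date of death to operate at all. A within-window reading is therefore possible and may well be what was meant.

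That does not settle the text. Protocol 13.1.4 hands death assignments to the SAP, and the specific rules already override 6.1.4 by rescoring days before death. So 6.1.4 cannot be assumed to supply the missing limit. Nor does the Day 28 horizon separate the Cox paragraphs from the eight counts: both kinds of rule have that horizon and both leave the death undated, so they should be treated alike.

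The objection on consequence largely stands. The study is exploratory, these outcomes are secondary, and Part 1 has no efficacy tests or p-values. The listings let a reader trace a recoded participant. Recruitment was paused with one Part 2 participant enrolled, so the Part 2 figures depend on resumption.

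**Conclusion.** As written, the rules give a wrong score for a death on Days 29–60: they replace complete Day 1–28 data and depart from the general death rule and from 8.2.6. One late death moves a raw Part 1 arm mean by up to 5.6 days (n = 5) or 9.33 days (n = 3). In a fully enrolled Part 2 arm the figure is about 0.78 to 0.22 days for d = 0 to 20. These sizes assume the planned allocation and a single late death, and d is illustrative.

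The stake is low, and a reader might infer more than the documents support:

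- *That Part 1 results are distorted.* No count of deaths on Days 29–60 is given. With none, the effect is zero. The length of follow-up after Day 28 says nothing about how many die then.
- *That the SAP intends late deaths to count.* It does not say so; it only fails to exclude them.
- *That the worst-total score is itself an error.* For deaths by Day 28 it is an explicit choice and is not questioned here.
- *That the reading would be chosen with the arms known.* The SAP is to be approved before any unblinded analysis, and SAP 10 places its changes before the Part 1 lock. This is a reason to settle the wording in time and no evidence of a problem.

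**What to change.** In 8.2.5 and 8.2.7–8.2.13, limit the rule to *participants that die on or before Day 28*, and add: *Participants who die after Day 28 keep their observed data through Day 28.* Put the same limit in the mortality sentences of the 8.2.4 and 8.2.5 Cox paragraphs. State in SAP 10, before the Part 1 database lock, that the limit governs the Part 1 summaries. Keep the worst-total score for deaths by Day 28. If late deaths are in fact meant to count, the SAP should say so and give the reason.

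The cost is a few words in eight rules, two matching Cox sentences and one line in SAP 10. No protocol change or new data are needed. SAP 10 already foresees a SAP amendment for Part 2, which can carry the same wording.

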8.2.11. Days Without Renal Stabilization

The number of days without renal stabilization from randomization through Day 28 will be summarized descriptively and analyzed using ANCOVA. The LS means will be presented along with the associated 95% CI within each treatment group. In comparing treatments, LS mean differences between treatments will be presented along with associated 95% CIs and p-values. In order to assign the worst total score for death, participants that die will have all days from randomization through day 28 treated as if they were on renal stabilization.

8.2.12. Days of Oxygen Support

The number of days of oxygen support from randomization through Day 28 will be summarized descriptively and analyzed using ANCOVA. The LS means will be presented along with the associated 95% CI within each treatment group. In comparing treatments, LS mean differences between treatments will be presented along with associated 95% CIs and p-values. In order to assign the worst total score for death, participants that die will have all days from randomization through day 28 treated as if they were on oxygen support.

8.2.13. Number of Healthcare Encounters

The number of healthcare encounters from randomization through Day 28 will be summarized descriptively and analyzed using ANCOVA. The LS means will be presented along with the associated 95% CI within each treatment group. In comparing treatments, LS mean differences between treatments will be presented along with associated 95% CIs and p-values. In order to assign the worst total score for death, participants that die will have all days from randomization through day 28 treated as if they had a healthcare encounter on each day.

8.3. Exploratory Efficacy Analysis

8.3.1. sPLA2

Observed sPLA2 values from randomization through Day 28 changes from baseline will be summarized descriptively and analyzed using ANCOVA. The LS means will be presented along with the associated 95% CI within each treatment group. In comparing treatments, LS mean differences in change from baseline between treatments will be presented along with associated 95% CIs and p-values.

8.3.2. Pharmacoeconomic Impacts

The pharmacoeconomic impacts of varespladib treatment will be reviewed in an exploratory manner using results from secondary endpoints to include number of healthcare encounters, number of hospitalization days, and number of days at elevated level of care (ICU), after randomization through Day 28.

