#### **13.1.4.4 Exploratory Analyses**

Change in sPLA2 from baseline through Day 28 will be analyzed using the same ANCOVA model as previously described for SpO2. The pharmacoeconomic impacts of varespladib treatment will be reviewed in an exploratory manner using results from secondary endpoints to include number of healthcare encounters, number of hospitalization days, and number of days at elevated level of care (ICU), all through Day 28.

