6.1.4. Handling of Dropouts or Missing Data

Withdrawn participants will not be replaced. Randomized participants withdrawn from the study may not reenter. The subject number for a withdrawn subject will not be reassigned to another subject.

Missing data for reasons other than death will, when possible, be derived from contemporaneous clinical data. If other clinical data are not available or not determinative of the outcome, data will be imputed based on the last available value (last observation carried forward).

Participants in the ITT population who experience death will have their data after death assigned as the worst possible value within a specific scale or in regard to duration or proportion as defined by the particular outcome. Participants who do not experience a particular event will not be excluded from the analysis of duration or time-to-event endpoints and will have an appropriate value assigned.

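### For Part 2 and the Combined Population, the pharmacoeconomic review reuses secondary results that score each death as 28 hospital days, 28 ICU days and a daily encounter, so it misstates the care used

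*SAP*

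**What the plan says.** SAP 8.3.2 has no derivation of its own. The review is to be "reviewed in an exploratory manner using results from secondary endpoints to include number of healthcare encounters, number of hospitalization days" and ICU days. Protocol 13.1.4.4 agrees: "The pharmacoeconomic impacts of varespladib treatment will be reviewed in an exploratory manner using results from secondary endpoints". The endpoint lists in the Protocol synopsis, Protocol section 6 and SAP 2.2.4 also define the pharmacoeconomic endpoint as a selection of secondary endpoints.

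Each of the three inputs carries its own death rule:

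- Hospital days (SAP 8.2.8): "participants that die will have all days from randomization through day 28 treated as if they had been in the hospital".
- ICU days (SAP 8.2.10): "participants that die will have all days from randomization through day 28 treated as if they had been spent in the ICU".
- Encounters (SAP 8.2.13): "participants that die will have all days from randomization through day 28 treated as if they had a healthcare encounter on each day".

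In each of these sections the rule shares a paragraph with both the descriptive summary and the ANCOVA, so it is not confined to the model. The general rule in SAP 6.1.4 is narrower. It says that participants who die "will have their data after death assigned as the worst possible value within a specific scale", which leaves data from before death alone.

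SAP section 10 records that recruitment paused with 18 participants in Part 1 and one in Part 2. For Part 1, exploratory outcomes are now to be listed only. It also commits to a protocol and SAP amendment for Part 2, prompted by the respiratory-support endpoints.

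**The concern.** The SAP gives the reason for the death rule: death must receive the worst total score, so that dying early does not look like a short stay. That suits an efficacy comparison. A pharmacoeconomic review has a different use for the same variables, because days and encounters stand for care delivered. Protocol 10.3.1.3 defines an encounter as an actual interaction with a provider. After death there are none, and a ward day before death is not an ICU day.

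If the scored results are carried over, part of any difference in resource use is a difference in deaths expressed as days of care. An imbalance in deaths, including a chance one in a small trial, would appear as ICU and hospital days saved that nobody would have used. Protocol 5.3 hopes the study will show the drug to be cost-effective, so these figures could well be read as evidence on that question.

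**Working it through.** **1. What the rule assigns.** Day 1 through Day 28 inclusive is 28 - 1 + 1 = 28 days. SAP 8.2.5 confirms this for a sister endpoint with the same kind of rule: those who die are "analyzed as having 28 days of COVID-level respiratory support". So each death enters as 28 hospital days, 28 ICU days and 28 encounters.

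**2. Overcount per death = 28 - actual days.** Illustrations, assuming the participant is in hospital from Day 1 until death:

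| Death on | True ICU days | Excess hospital days | Excess ICU days |
|---|---|---|---|
| Day 7 | 3 | 21 | 25 |
| Day 14 | 7 | 14 | 21 |
| Day 28 | 28 | 0 | 0 |

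The overcount is zero only when all 28 days were truly used.

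**3. Use before death is overwritten too.** For a Day 14 death after 7 ICU days, observed use is 7. The general rule in SAP 6.1.4 would give 7 + 14 = 21. SAP 8.2.10 gives 28.

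**4. Effect on one arm's mean = deaths x (28 - actual days) / 36.** The 36 is 72 / 2, from SAP 3.2. The documents give no mortality or timing of death, so I assume 1 to 9 deaths per arm, on Day 7, 14 or 21, with ICU care on half the days before death.

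- Hospital days: from 1 x 7 / 36 = 0.19 to 9 x 21 / 36 = 5.25.
- ICU days: from 1 x 17.5 / 36 = 0.49 to 9 x 24.5 / 36 = 6.1.

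**5. Effect on the ICU-day difference.** Assume 5 deaths on placebo and 2 on varespladib, with the same mean true ICU days per death in both arms:

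| True ICU days per death (assumed) | Shift from scoring alone |
|---|---|
| 3 | 3 x 25 / 36 = 2.08 |
| 8 | 3 x 20 / 36 = 1.67 |
| 14 | 3 x 14 / 36 = 1.17 |

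All three shifts favour the arm with fewer deaths.

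**6. Direction.** Let survivors average S days in both arms and those who die average d. The difference, varespladib minus placebo, is (difference in deaths) x (d - S) / 36 in truth, and (difference in deaths) x (28 - S) / 36 as scored. For hospital days with 3 v 6 deaths and S = 10 (assumed):

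| Day of death | True difference | Scored difference |
|---|---|---|
| Day 7 | -3 x (7 - 10) / 36 = +0.25 | -3 x 18 / 36 = -1.50 |
| Day 14 | -3 x (14 - 10) / 36 = -0.33 | -1.50 |
| Day 21 | -3 x (21 - 10) / 36 = -0.92 | -1.50 |

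In this set-up the sign reverses only when those who die use fewer days than survivors (d below S). Otherwise a real difference is exaggerated. With 4 v 4 deaths at the same time, the true and scored differences are both zero, and only the arm means are inflated.

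**7. Encounters.** The Protocol 10.3.1.3 definition permits more than one encounter a day and also counts escalations of care. A score of 28 is therefore not a ceiling and could fall below actual use.

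These are simple arm means; covariate adjustment is not modelled.

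**The case against.** **The plan follows the protocol.** The protocol itself defines the pharmacoeconomic endpoint as selected secondary endpoints, so SAP 8.3.2 is consistent with it. A reader might infer that the two documents contradict each other; they do not. What stands is that the chosen quantity does not measure resource use.

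**Unscored data will exist.** Protocol 13.1 promises an observed-cases tabulation of primary and secondary endpoints, all data are listed, and deaths are analysed and listed separately. This mitigates the problem without curing it. The observed-cases statement is not repeated in the SAP or linked to this review, and the SAP places the death rule beside the descriptive summaries.

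**Observed use has the opposite artefact.** An early death then looks like a saving. This is true, and it is why deaths must be shown next to observed use.

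**The review is exploratory and Part 2 is paused.** No unit costs, test or decision rule attaches to the review, and the problem bites only if Part 2 goes ahead. That limits its weight but does not make the figures correct.

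Three stronger readings are tempting, and the documents do not support them:

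- *Part 1 is distorted.* In an arm of 5, one death with an assumed 8 true ICU days raises the mean by 20 / 5 = 4.0 days. That figure describes the secondary ICU-day summary, where the scoring is deliberate. SAP section 10 plans no summarised pharmacoeconomic comparison for Part 1.
- *The comparison is merely one of mortality, with the wrong sign.* Reversal depends on assumptions. With 8 ICU days per death, the ICU difference reverses only if survivors average more than 8. If they average 2 (assumed), the true difference for 5 v 2 deaths is 3 x (8 - 2) / 36 = 0.5 days in the same direction as the scored one.
- *Encounters are always overcounted.* They may be undercounted.

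**Conclusion.** The concern holds for the pharmacoeconomic review in Part 2 and the Combined Population. As written, the review reports care that was not delivered. Hospital and ICU days are overstated by 28 minus actual days for each death, and encounters are misstated in either direction. The between-arm difference is biased when the number of deaths or the use before death differs between arms. It is unbiased when both match, although the arm means remain inflated.

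For 36 per arm and 5 v 2 deaths, the scoring alone moves the ICU-day difference by about 1.2 to 2.1 days per participant over an assumed 3 to 14 true ICU days per death. The existence of the overcount follows from the text. Its size, and any change of sign, rest on assumed mortality, timing and survivor stay, none of which the documents give.

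One related wording point: SAP 8.2.8, 8.2.10 and 8.2.13 do not limit the rule to deaths by Day 28, whereas the SpO2 rule in SAP 8.2.6 does. Read literally, a death between Day 29 and Day 60 would also score 28.

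**What to change.** Make the change in the Part 2 protocol and SAP amendment that SAP section 10 already foresees.

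- In SAP 8.3.2 and Protocol 13.1.4.4, state that the pharmacoeconomic review uses observed hospital days, observed ICU days and observed encounters from randomization to death or Day 28, whichever comes first, with no value imputed for death. Require the number of deaths per arm in the same table.
- Align the endpoint wording in the Protocol synopsis, Protocol section 6 and SAP 2.2.4 (headed as pharmacokinetic but listing the pharmacoeconomic endpoints). Otherwise the phrase about selected secondary endpoints would contradict the new text.
- Keep the worst-value death scoring in SAP 8.2.8, 8.2.10 and 8.2.13 for the efficacy comparison.

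The cost is one extra derived variable per endpoint and a few matching edits. No new data are needed: hospital and ICU days are already required for the secondary endpoints, and Protocol 10.3.1.3 has encounters recorded through Day 60. The downside is that observed use cannot be read alone, because early death shortens it; the deaths reported alongside are an essential part of the change.
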